##### 72 hour reporting

For the discovery of an unexpected serious adverse event thought to be related to study drug, the Investigator(s) will notify the Chair of the DSMB by email within 72 hours.

### 8.5 STUDY HALTING RULES

Please see separate DSMB Charter

### 8.6 SAFETY OVERSIGHT

Please see separate DSMB Charter

## 9 CLINICAL MONITORING

Sites will be remotely monitored. Should the need arise for further investigation, an independent monitor will be appointed to visit sites. Each site has extensive clinical trial experience and the expectation for this need is low. Nevertheless, the PI will visit each site at least once per year for meeting with study staff and random surveillance.

## 10 STATISTICAL CONSIDERATIONS

## 10.1 STATISTICAL AND ANALYTICAL PLANS

Previous work demonstrates the value of B-lines to improve both diagnosis and prognosis in AHF. Whether targeting B-lines to guide therapy results in improved outcomes, is unknown. Prior to examining outcomes however, a key step is required: does LUS guided, protocol-driven treatment result in less B-lines than usual care? In other words, can B-lines be actively targeted as a treatment endpoint?

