**Prior Studies**

*Sonographic evidence of pulmonary congestion is associated with worse outcomes.*

We performed a single center pilot study of 44 patients who presented to the ED with dyspnea, evidence of B lines by LUS, and were admitted for AHF. Patients underwent LUS imaging during the ED (T0), within 24 hours (T1) and at discharge (Td). Vital status was determined by phone follow up within 90 days. Using a pre-specified cut-off of 15 B-lines as a marker of persistent pulmonary congestion, 50% of patients had evidence of EVLW at Td. The 28 sector scoring method was utilized. The average number of B-lines at T0 was 78±47 with a statistically significant reduction at T1 (44±33, p<.001) and Td (26±26, p<.05). (See Figure 2) Thirty-two patients (73%) were successfully contacted for follow-up.

[figure not shown]
[figure not shown]

Figure 3: Prognostic Value of LUS

Subjects at risk

— B-lines ≤15	60	60	60	60	59	59	59
- - - B-lines >15	40	37	33	31	31	28	27

During the follow-up period (median: 58 days, interquartile range: 44-82 days) 15 events occurred: 2 deaths and 12 all-cause re-hospitalizations. In the subset of patients who experienced events during follow-up, 93% were discharged with persistent presence of pulmonary congestion (> 15 B-lines) as measured by LUS.

Another pilot study of patients (n=100) admitted to a cardiology ward for shortness of breath and clinical concern for AHF demonstrated a statistically significant reduction in B lines at discharge (20+/- 23) vs. admission (48+/-48, p<.0001). At 6-month follow up, patients with ≥ 15 B-lines at discharge were significantly more likely to be re-hospitalized. (HR 11.7 (95% CI 1.3-106.6) (See Figure 3). In 27% of patients with >30 B-lines, no rales were reported by auscultation.

Additional work performed by one our study team members, [name], demonstrated a strong correlation between LUS B-lines and patients undergoing dialysis. This proof of concept supports B-lines as responsive to the removal of fluid. Coiro et.al. recently published a study of LUS performed throughout hospitalization, demonstrating the prognostic significance of residual congestion, as measured by B-lines.

Patients with  $\geq 30$  B lines had significantly worse combined outcome of all-cause mortality and HF re-hospitalizations at 90 days.

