### 10.4.3 ANALYSIS OF THE PRIMARY EFFICACY ENDPOINT(S)

The comparison of binary endpoints (B-lines < 15) will be performed using Chi-square or Fishers exact test, as appropriate.

Potential covariates will also be considered in a logistic regression setting to improve precision, which includes baseline co-morbidities, baseline medications (in particular guideline recommended therapies) in-hospital medications, baseline renal function, serum sodium, natriuretic peptide levels, troponin levels, renal function, baseline blood pressure, and discharge medications. Variables such as physical exam, other vital signs, and hemoconcentration may also be included. For NT-proBNP, a percent change greater than 30% and its association with the primary endpoint will be analyzed. This is based on previous work suggesting a 30% change was a key discriminatory threshold for mortality. For hemoconcentration, any increase in value in both hematocrit and hemoglobin during hospitalization will be considered positive. These covariates are known markers of risk and are standard of care assessments for the vast majority of AHF admissions. Covariates with univariately significant association with the outcome will be included together with the treatment indicator in a logistic regression model. Due to limited sample size, we will limit the number of covariates (including treatment indicator) such that there is 10 events per covariate.

---

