### 10.4.4 ANALYSIS OF THE EXPLORATORY ENDPOINT(S)

*DAOOH*: Will be compared using T test or Wilcoxon rank-sum test, as appropriate.

If the distribution of 30 or 90 days *DAOOH* is skewed, the T test may not perform satisfactorily. An alternative approach to evaluate the robustness of the analysis, is to treat *DAOOH* as an ordinal outcome and use the proportional odds (PO) regression model to compare the two arms. The PO model is a generalization of the Wilcoxon (Mann-Whitney) test to estimate the shift in the underlying distribution of *DAOOH* by the intervention. The PO regression allows for adjustment of baseline covariates to enhance power.

We will examine the distribution of B-lines measurements for the groups with and without events separately. Both absolute number and relative change will be evaluated. Receiver Operating Characteristic (ROC) curves will be plotted together with area under the curve (AUC) calculated to understand the prediction performance of the B-line measurements. Sensitivity, specificity, positive and negative predictive values will be computed at a number of thresholds of B-line measurements to understand the trade-off between false positive and false negative. Confidence intervals of statistical measures will be constructed using the bootstrap method. Although 15 B-lines have been previously identified as a valid threshold, an alternative number may be more useful in the ED setting.

For reproducibility analysis, generalized linear mixed-effects models will be fitted to estimate the inter- and intra-observer variability, where both patients and observers are treated as random effects.

We will compare parameters used to identify congestion. This will include a comparison between B-lines measurements and other markers, such as physical exam, NTproBNP, eGFR, and hemoglobin/hematocrit. Bootstrap method will be used for the comparison to account for correlations between the markers and the B-line measurements. We will consider two strategies to explore potential multivariate models:

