### 10.5 SAMPLE SIZE

Our preliminary data suggest that 25% of patients in the usual care arm will have < 15 B lines at the conclusion of ED AHF management. With 59 patients in each of the two arms, we will have 81% power to detect an effect size of 2 (i.e. 25% in the usual care versus 50% in the strategy care), where the type I error rate is controlled at 0.05 (two-sided). Considering a conservative 10% drop-out rate, we will need a total of 130 subjects.

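### B-lines are compared between arms only through the 15-line threshold, and the baseline count is not a pre-specified covariate; both gaps can be closed without new data

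*Combined protocol and SAP*

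**What the plan says.** Section 10.1 puts the question as "does LUS guided, protocol-driven treatment result in less B-lines than usual care", and then restates it as whether B-lines can serve as a treatment target. Hypothesis 1 in Section 10.2 defines less congestion by the 15-line threshold.

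- **Primary analysis (Section 10.4.3).** "The comparison of binary endpoints (B-lines < 15) will be performed using Chi-square" or Fisher's exact test.
- **Logistic model (Section 10.4.3).** Its declared aim is better precision. The candidate list covers co-morbidities, medications, renal function, biomarkers and blood pressure, and includes in-hospital and discharge medications. Baseline B-line count is not named. Candidates enter if univariately significant, within a limit of 10 events per term, treatment included.
- **Exploratory B-line endpoints (Section 4.2.2, Table 3).** Time to fall below 15, and being below 15 at 24 hours and at discharge.
- **The count itself (Section 10.4.4).** "We will examine the distribution of B-lines measurements for the groups with and without events separately". Here, events are later outcomes, so this is a prognostic analysis and not a comparison of arms.
- **Serial LUS (Section 10.2).** It is to be assessed, but no variable, time point, model or arm contrast is given.

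The data will exist. Section 17.3 sums the count over 8 sectors at each scan, and Section 5.1 requires more than 15 lines at the first scan.

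**The concern.** Two things are missing.

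First, the plan looks for covariates to gain precision but passes over the baseline value of the measure that defines the endpoint. A patient who enters just above 15 lines is plausibly nearer the target than one who enters with several times as many. The candidate list is open-ended, so the baseline count could still be added, but nothing commits to it. Even if it were listed, it would have to pass a data-driven screen. Some variables that are listed, such as discharge medications, arise after randomisation and cannot serve as baseline adjustment.

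Second, no analysis estimates how far the count differs between arms. A patient who falls from 70 to 20 lines and one who stays at 70 are both failures. The pilot exists to inform a definitive trial (Section 3), and a result at a single cut gives little on the shape of the effect. The protocol is itself tentative about that cut: Section 10.4.4 allows that another number may suit the ED better. In the 44-patient pilot that used 15, "The 28 sector scoring method was utilized", whereas this trial scores 8 zones.

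**Working it through.** **Inputs from Section 10.5.** "With 59 patients in each of the two arms, we will have 81% power to detect an effect size of 2", with "25% in the usual care versus 50% in the strategy care", two-sided alpha 0.05.

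**1. The plan's own figure.** The pooled proportion is (0.25 + 0.50)/2 = 0.375.

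Power = Φ{[0.25 − 1.96·√(2·0.375·0.625/59)] / √[(0.25·0.75 + 0.50·0.50)/59]} = Φ(0.874) = 80.9%. The stated 81% reproduces.

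**2. Room in the logistic model.** Expected responders are 59·0.25 + 59·0.50 = 44. At 10 events per term, that allows four terms including treatment. Treatment and baseline count use two.

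**3. Power on the count if the whole distribution shifts.** Assume a normal (log) count. Moving 25% to 50% then needs a shift of d = z(0.50) − z(0.25) = 0.674 SD. Let r be the correlation between baseline and follow-up counts. The documents give no r and no SD for 8-zone scoring, so r is shown as a range. The noncentrality is d·√(59/2)/√(1 − r²):

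- Unadjusted: 0.674·5.431 = 3.663. Power is Φ(3.663 − 1.96) = 95.6%, or 95.3% from the t distribution.
- r = 0.3: 97.0%.
- r = 0.5: 3.663/0.866 = 4.230, giving 98.8% (98.7% from the t distribution).
- r = 0.7: 99.9%.

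If the true rates are 25% and 40%, the figures are 41% (binary), 62–63% (count) and 75% (count, adjusted, r = 0.5).

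**4. Does this survive a different effect shape?** Under Section 4.1, guided treatment runs until the target is reached, 6 hours have passed or the patient has left the ED. An equal shift in everyone is therefore only one possibility. Three shapes were simulated with 59 per arm. Counts were rounded log-normal with log-SD 0.8, and 25% of usual-care patients met the target. Each shape produces about 50% responders in the guided arm:

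- *Whole shift:* every guided patient's log count falls by 0.674 SD.
- *Treat-to-target:* a random third of would-be non-responders in the guided arm is brought to 10–15 lines (25% + 75%/3 = 50%).
- *Extreme:* only patients near the threshold move, to just below it.

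Power, ranges over r = 0.3–0.7:

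| Effect shape | Chi-square | Logistic, baseline fixed | Log-count ANCOVA |
|---|---|---|---|
| Whole shift | about 80–82% | about 82–93% | 97–99.7% |
| Treat-to-target | about 80–81% | about 81–88% | about 50–67% |
| Extreme | 80–82% | 83–92% | 16–23% |

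With no treatment effect, all tests rejected in about 4–6% of runs. At r = 0.3 the logistic gain is only a point or two, close to simulation error; it becomes material from about r = 0.5.

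**5. Is the count uniquely defined?** The B-line counting rules in Section 17.1 set a maximum of 20 per sector, and Section 17.3 sets 10. Over 8 sectors, the total is capped at 160 or at 80. Any count analysis depends on which applies.

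**The case against.** The strongest reply is that the threshold is the question. Section 10.1 goes on to ask whether B-lines can be targeted, Hypothesis 1 is defined at 15, and Section 2.2 gives prognostic data for that value. The binary primary is valid and its power reproduces. This stands, and it is why the primary endpoint should not change.

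A reader might infer that the plan simply discards power by splitting the count. The documents do not support that. The gain in step 3 requires treatment to move the whole distribution, including patients already below 15. The trial treats to a target, and under that kind of effect the ordering reverses: about 50–67% for the adjusted count against about 80–81% for the binary test.

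Three further replies have force:

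- The plan is not limited to one cut at one time. Table 3 adds time to threshold and two later time points, although all use the same threshold.
- The documents give no correlation, so nothing shows that baseline count is the strongest predictor. The gain from adjustment is therefore stated as a range.
- The log scale weights low counts heavily. On log(count + 1), a fall from 14 to 3 (15/4 = 3.75) equals a fall from 59 to 15 (60/16 = 3.75), although guided treatment does not pursue reductions below target. This favours offering a rank-based alternative.

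The 28-sector origin of the pilot's scoring is a separate matter about the cut-off. A supportive count analysis would not settle it.

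**Conclusion.** The point holds as a matter of precision and description. It does not show that the primary analysis is invalid. No planned analysis compares the count between arms, and the baseline count is not a committed covariate.

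Fixing the baseline count in the logistic model did not lower power under any effect shape tried. The gain runs from roughly nothing at r = 0.3 to about 12 points at r = 0.7 under a whole shift (81% to 93%), and about 7 points under treat-to-target (81% to 88%). These sizes rest on the assumed r and log-normal counts.

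The count comparison is worth having as a supportive estimate. Whether it would be more or less powerful than the binary test depends on the effect shape, which the documents do not give. Learning that shape is itself useful for designing the definitive trial.

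**What to change.** 1. In Section 10.4.3, pre-specify log baseline B-line count as a fixed covariate in the logistic model for the primary endpoint, exempt from univariate selection. State whether the unadjusted test or this model carries the primary conclusion, since the power gain belongs to the adjusted test.
2. In Section 10.4.4, add one supportive between-arm analysis of the 6-hour count, with no alpha claimed. Use ANCOVA on log(B-lines + 1) or a rank-based model, with baseline count and site as covariates, and report the difference with its 95% CI. Site belongs in the model because randomisation is blocked within site (Section 10.6.1).
3. Before either analysis, reconcile the per-sector maximum in Sections 17.1 and 17.3 and apply one scoring rule to both scans. Also align the endpoint, which is at or below 15 in Section 4.2.1 and below 15 in Sections 10.2, 10.4.3 and 10.5.

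The cost is SAP wording and one additional model on data already being collected. The primary endpoint, sample size and alpha are unchanged.

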## 10.2 STATISTICAL HYPOTHESES

- *Hypothesis 1: LUS guided patients will have less congestion, defined by LUS B-lines <15, than usual care patients at 6 hours after start of treatment. Other measures of congestion, such as serial LUS during hospitalization, physical exam, NTproBNP, and hemoglobin/hematocrit levels will be assessed to determine the superiority or additive value of LUS.*
- *Exploratory Hypothesis: Strategy-of-care patients will have more days alive and out of hospital (DAOOH) at 30 days.*
  - *Strategy-of-care patients will have more days alive and out of hospital (DAOOH) at 90 days.*
- *Hypothesis 2: Each site (n=4) will enroll ~2 patient per month for 18 months.*

## 10.3 ANALYSIS DATASETS

The Full Analysis Set (FAS) will include all randomized patients. In accordance with the intent-to-treat principle, patients will be analyzed by the group to which they were randomized. Misrandomized patients (patients randomized in error who did not receive any study intervention) will be excluded. Analyses in the FAS will constitute the main efficacy results for the primary and secondary study efficacy endpoints.

The Per Protocol Set (PPS) will be a subset of the FAS and will exclude patients with major protocol violations. The major protocol violations that will result in exclusion from the PPS will be identified prior to unblinding the treatment assignments for final analysis. Patients will be analyzed in the treatment group to which they were randomized. Results of analyses in this analysis population will support the primary efficacy analyses in the FAS.

## 10.4 DESCRIPTION OF STATISTICAL METHODS

### 10.4.1 GENERAL APPROACH

Unless stated otherwise, two-sided p values < 0.05 will be considered statistically significant, without regard to multiple comparisons. Statistical tables and listings and analyses will be produced using SAS® release 9.1 or later (SAS Institute, Inc, Cary, NC, USA) or other validated statistical software.

### 10.4.2 BASELINE DESCRIPTIVE STATISTICS

We will tabulate baseline characteristics of the two trial arms for potential imbalance in variables. Continuous variables will be summarized by typical parameters such as mean, standard deviation and range and compared using two-sample T test (if the normality assumption holds) or Wilcoxon rank-sum test (if the normality assumption does not hold). Normality of distribution will be determined using the Kolmogorov-Smirnov goodness-of-fit test. Categorical data will be summarized by frequency and percentage and analyzed using the Chi-square or Fishers exact test, as appropriate.

The use of prior and concomitant medications will be summarized. The use and doses of IV and oral loop diuretics in furosemide equivalents will be summarized by treatment group. Other concomitant medications will be coded using WHO Drug and summarized by treatment group according to Anatomic Therapeutic Classification and preferred term.

---

### 10.4.3 ANALYSIS OF THE PRIMARY EFFICACY ENDPOINT(S)

The comparison of binary endpoints (B-lines < 15) will be performed using Chi-square or Fishers exact test, as appropriate.

Potential covariates will also be considered in a logistic regression setting to improve precision, which includes baseline co-morbidities, baseline medications (in particular guideline recommended therapies) in-hospital medications, baseline renal function, serum sodium, natriuretic peptide levels, troponin levels, renal function, baseline blood pressure, and discharge medications. Variables such as physical exam, other vital signs, and hemoconcentration may also be included. For NT-proBNP, a percent change greater than 30% and its association with the primary endpoint will be analyzed. This is based on previous work suggesting a 30% change was a key discriminatory threshold for mortality. For hemoconcentration, any increase in value in both hematocrit and hemoglobin during hospitalization will be considered positive. These covariates are known markers of risk and are standard of care assessments for the vast majority of AHF admissions. Covariates with univariately significant association with the outcome will be included together with the treatment indicator in a logistic regression model. Due to limited sample size, we will limit the number of covariates (including treatment indicator) such that there is 10 events per covariate.

---

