### PROTOCOL SUMMARY

**Title:** B-lines Lung Ultrasound Guided ED Management of Acute Heart Failure (BLUSHED-AHF)

**Précis:** Of the one million admissions for AHF in the US, approximately 80% are initially managed in the ED. Outcomes from AHF are poor: nearly 25% are dead or re-hospitalized within 30 days of discharge. The evidence base to treat AHF is limited. In fact, there are no pharmacologic therapies with Class I, Level A guideline recommendations. The acute

[figure not shown]
treatment of patients today is largely the same as 40 years ago. This proposal aims to build the evidence base for ED AHF care.

Using a multi-center, randomized controlled design, this pilot study will test whether a strategy of care – lung ultrasound (LUS) guided protocol-driven AHF therapy – outperforms usual care at reducing congestion in the ED setting.

Objectives:	
1. To determine whether a strategy of care – early LUS guided, protocol-driven ED AHF therapy – leads to more rapid resolution of congestion.
 
2. To demonstrate feasibility of recruitment and compliance with study protocol to inform future study design and enrollment projections

Endpoint	B-lines $\leq$ 15 at the conclusion of ED AHF management or maximum of 6 hours after enrollment, whichever comes first.
Population:	Emergency department (ED) AHF patients. All patients who meet inclusion and no exclusion criteria will be enrolled within 3 hours of presentation.
Phase:	2
Number of Sites enrolling participants:	Three sites (4 total hospitals). Projected sample size, n=130.
Description of Study Agent:	Strategy of Care: LUS guided protocol-driven ED AHF care vs. usual care.
Study Duration:	2 years. There will be three months of start up, and three months of study conclusion work. Enrollment will occur over 18 months, which equals 7.2 patients month. With 4 sites (2 at IU, 1 at Detroit, and 1 at Vanderbilt), this equals 1.8 patients/month.
Participant Duration:	90 days post discharge

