### 4 STUDY DESIGN AND ENDPOINTS

#### 4.1 DESCRIPTION OF THE STUDY DESIGN

A multi-center, prospective, randomized, controlled, unblinded strategy-of-care pilot trial. All potential ED patients will receive an initial LUS scan. Performing LUS is within the standard of care and will be done at no cost to patients. It is not frequently used however, either for diagnosis, prognosis, or to guide clinical therapy. However, treating clinicians will be blinded to these results to minimize contamination of the usual care arm. If clinicians choose to perform their own LUS, those patients will not be excluded. Patients who provide written informed consent and meet all inclusion and no exclusion criteria will be randomized 1:1 to our LUS-guided strategy-of-care vs. usual care. While no further LUS guided intervention will occur for usual care patients, similar to our LUS-guided arm, serial LUS assessments will occur throughout hospitalization as well as pre-specified biomarkers and physical exam. For patients randomized to the strategy-of-care arm, the LUS guided protocol will be initiated and continued until there is a decrease in B-lines to  $\leq 15$  or 6 hours of care has been delivered or patient has left the ED, whichever comes first. Trained research personnel will acquire LUS images. All images will be stored and overread by an independent, expert ultrasonographer blinded to treatment arm.

Safety of patients are paramount. If a potential life threatening etiology is identified, the clinical team will be made aware immediately, irrespective of randomization arm. These occurrences will be recorded in the eCRF. While this will be a rare event, we will a priori establish that an additional patient will be accrued into the study and an additional modified intent to treat population for analysis will be performed, excluding these patients where a life-threatening etiology was identified (i.e. pericardial tamponade).

For patients who do NOT meet eligibility criteria, the results of their LUS will be provided to the clinical team as requested, as these patients are no longer at risk for contamination of the usual care arm.

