#### 4.2.1 PRIMARY ENDPOINT

B-lines  $\leq 15$  at the conclusion of ED AHF management (i.e. patient has left the ED) or maximum of 6 hours after enrollment, whichever comes first.

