## 5 STUDY ENROLLMENT AND WITHDRAWAL

### 5.1 PARTICIPANT INCLUSION CRITERIA

- 1) Age  $\geq 21$  years
- 2) Presents with shortness of breath at rest or with minimal exertion
- 3) Clinical diagnosis of AHF and presence of > 15 total bilateral B-lines distributed in at least 4 zones on initial LUS
- 4) Hx of chronic HF and any one of the following:
  - i. Chest radiograph consistent with AHF
  - ii. Jugular venous distension
  - iii. Pulmonary rales on auscultation
  - iv. Lower extremity edema

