### *Screen Failures:*

Patients who sign an informed consent but who are not randomized will be considered Screen Failures. Only data for randomized patients will be entered into the CRF. Serious adverse events should be reported for these patients from the time the ICF is signed through the time that the patient is declared a screen failure. One expected reason for screen failure will be the absence of > 15 B-lines at baseline.

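### The primary endpoint is defined as B-lines ≤15, but the hypothesis, the primary test and the planning rate use <15, so a count of exactly 15 is a success in one place and a failure in the other

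*Combined protocol and SAP*

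**What the plan says.** Two cut-offs appear in the current text.

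**At or below 15 (or its complement, above 15):**
- Protocol summary, endpoint row: "B-lines $\leq$ 15 at the conclusion of ED AHF management or maximum of 6 hours after enrollment, whichever comes first".
- Section 4.2.1, the primary endpoint: "B-lines $\leq 15$ at the conclusion of ED AHF management".
- Section 4.1, the LUS-guided protocol: "continued until there is a decrease in B-lines to $\leq 15$ or 6 hours of care has been delivered".
- Section 5.1, entry: "presence of > 15 total bilateral B-lines distributed in at least 4 zones on initial LUS".
- Section 5.3, screen failures: "One expected reason for screen failure will be the absence of > 15 B-lines at baseline".

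**Strictly below 15:**
- Section 10.2, Hypothesis 1: "LUS guided patients will have less congestion, defined by LUS B-lines <15".
- Section 10.4.3, the primary analysis: "The comparison of binary endpoints (B-lines < 15) will be performed using Chi-square or Fishers exact test, as appropriate".
- Section 10.5, the planning rate: "25% of patients in the usual care arm will have < 15 B lines at the conclusion of ED AHF management".
- Section 4.2.2, Table 3: the two exploratory rows on time to the B-line threshold and on status at 24 hours and discharge.

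None of this is amendment-log text, and no section says which cut-off prevails.

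**The concern.** The split is systematic. The design and endpoint sections use ≤15, while every statistical section that names a cut-off uses <15. A programmer working from section 10 would code one responder variable, and a reader of section 4 would expect another.

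The <15 version also conflicts with the rest of the design. A patient with exactly 15 B-lines at baseline has too few to be enrolled. A patient in the LUS arm who falls to exactly 15 has met the strategy's stated target. Section 10.4.3 would nevertheless score that patient as still congested at the endpoint.

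At stake is the primary p-value, which can depend on which section is followed. If the choice is made after results are known, it is open to selection or to the suspicion of it. Withholding Core Lab readings from investigators until lock (17.3, Image Review) is only a partial guard, because the trial is unblinded (10.6.1) and sites record their own counts (17.1 and 17.3).

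**Working it through.** **1. The plan's own figure.** Section 10.5 gives 59 per arm, 25% v 50%, two-sided 0.05, and 81% power. With the pooled two-proportion formula, p̄ = 0.375 and

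power = Φ{[0.25 − 1.96·√(2·0.375·0.625/59)] / √[(0.25·0.75 + 0.50·0.50)/59]} = 80.9%.

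This reproduces the stated figure. The total also reproduces: 118 × 1.1 = 129.8, hence 130.

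**2. Can a score be exactly 15?** Yes. B-lines are counted individually in each sector (17.1) and summed over 8 sectors (17.3), so totals are whole numbers.

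**3. How many patients might score exactly 15?** The documents do not say, so the shares are assumptions. Two scenarios fix the share at 1% or 2% in each arm. Three use log-normal counts X with P(X < 15.5) set to 25% and 50%, where σ = √ln(1 + CV²) and the share at 15 is P(14.5 < X < 15.5). For CV 0.6, σ = 0.5545 and the medians are 22.5 (usual care) and 15.5 (LUS). The shares are then 3.66% and 4.79%. Expected number at 15 = 59 × (sum of the two shares).

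**4. How often do the two cut-offs disagree at 0.05?** Exact enumeration at 59 per arm: the number ≤15 is binomial with 25% or 50%, and the number <15 is binomial within it.

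| Share at 15, usual care / LUS | Expected of 118 | Disagree, chi-square | Only ≤15 significant | Only <15 significant | Disagree, Fisher |
|---|---|---|---|---|---|
| 1% / 1% | 1.18 | 4.12% | 1.81% | 2.31% | 4.78% |
| 2% / 2% | 2.36 | 6.28% | 2.59% | 3.69% | 7.31% |
| 3.66% / 4.79% (CV 0.6) | 4.98 | 9.59% | 5.30% | 4.29% | 11.10% |
| 2.67% / 3.45% (CV 0.9) | 3.61 | 8.06% | 4.40% | 3.67% | 9.33% |
| 2.19% / 2.81% (CV 1.2) | 2.95 | 7.22% | 3.91% | 3.31% | 8.35% |

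The chi-square test is uncorrected. The chance that at least one patient scores exactly 15 runs from 69.5% (first row) to 99.4% (third row).

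**5. A one-patient illustration.** With chi-square, 15/59 v 26/59 gives p = 0.033 and 15/59 v 25/59 gives p = 0.052. With Fisher the crossing is one count higher: 15 v 27 gives 0.034 and 15 v 26 gives 0.053.

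**6. Power.** If 25%/50% are ≤15 rates and <15 is tested, power is 81.4% (1%/1%), 81.8% (2%/2%) and 79.4% to 80.1% (log-normal). If they are <15 rates and ≤15 is tested, it is 80.5%, 80.1% and 81.6% to 82.0% (log-normal recalibrated at 14.5). As an extreme bound, suppose scores of 15 occur only in the LUS arm, whose protocol stops at ≤15, and 25%/50% are ≤15 rates. Testing <15 then means 25% v 49%, 48% or 45%, with power 77.8%, 74.3% or 62.7%.

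**7. Cost of choosing afterwards.** With a true 25% in both arms, either cut-off used alone has a type I error of about 5.2% to 5.3% (uncorrected chi-square). Taking whichever is significant raises it to 6.2%, 6.8% or 7.5% for assumed shares of 1%, 2% or 4% at exactly 15.

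**The case against.** The strongest reply is that <15 is loose typing. Section 4.2.1 is headed as the primary endpoint, and the summary, the treatment target, the entry rule and the screen-failure rule all agree with it. The prior-studies text in 2.2 shows the same looseness: the 100-patient study is described with ≥15 for the congested group, while the legend of its figure splits the same 100 patients at ≤15 (60) and >15 (40). On this view the analyst already has a defined endpoint to follow.

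Further points on that side:
- Either cut-off used alone gives a valid test, and the disagreement runs in both directions.
- The overread is blinded to arm (4.1), which limits the room for selection.
- One line is within measurement error. The best inter-observer variability quoted in 2.2 is 7.4%, and 0.074 × 15 is about 1.1 lines.
- The one-patient example moves a patient in one arm only. Moving one in each arm from 15 v 26 gives 14 v 25 and p = 0.031, still significant.
- This is a pilot, and the shares at exactly 15 are assumed. White-out is scored by proportion, so real counts may cluster in ways that a smooth curve misses.

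Most of this stands, and it bears on how large the effect is. It does not remove the conflict. Shorthand is the likeliest explanation, but the text never says so, and the section that specifies the primary test is one of those using <15. Measurement error affects both definitions and does not decide between them. A pilot with a two-sided 0.05 primary test still needs one responder rule.

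**Conclusion.** The concern holds. The primary responder has two definitions in the current text, and they classify a count of exactly 15 in opposite ways. That follows from the wording alone and needs no assumption.

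The size does rest on assumptions. Across the five scenarios, one to five of 118 patients score exactly 15, and the cut-offs disagree on significance in about 4% to 10% of trials with chi-square or 5% to 11% with Fisher. The case does not depend on loss of power: the sample-size arithmetic reproduces, and power is 79.4% to 82.0% when the shares are similar by arm. Larger movements require scores of 15 to fall mainly in one arm, which the documents neither show nor exclude. The two Table 3 rows are exploratory and do not affect the primary test.

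Because this is the decision rule of the primary test, it must be settled before lock.

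**What to change.** Before database lock:

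1. Change the cut-off in 10.2, 10.4.3, 10.5 and Table 3 to ≤15, as in 4.2.1, and state that a count of exactly 15 is a success.
2. Check whether the preliminary 25% rate was derived as <15 or ≤15, and label it in 10.5.
3. Report the number of patients at exactly 15 by arm, and give the <15 result as a sensitivity analysis.

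The first step resolves the conflict. The other two let readers see whether it mattered. The cost is wording in four sections, one look at the preliminary data and one extra table. No new data are needed, and no change to the sample size or the treatment target is proposed.
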